identified locations. All data collection activities will comply with the recommended social distancing requirements currently in place at the time.

Quantitative study measures will be implemented through the use of on-line REDCAP survey software and is available to interested individuals through an on-line link. Participants can complete the survey in any environment in which they have access to the Internet (i.e., public library; home; work). If the interested participant does not have a device to access the Internet and the survey or communicate with the researcher to indicate their responses, the primary researcher will meet them a place identified as convenient for the participant with the necessary equipment to complete the survey (i.e., laptop computer with Internet connectivity).

8) Prior Approvals

N/A

9) Study Design

Recruitment Methods

Recruitment will occur through local community partners, which include Philadelphia Independence Network, Community Integrated Services, Carousel Connection GRASP, ASERT, Philadelphia the Institute of Disability at Temple University, and the Philadelphia Area Charter School. We have an established relationship with all of these organizations. An introductory recruitment e-mail (see materials submitted with IRB protocol) will be sent to potential participants through the organization, which includes a link to the survey questions on REDCAP.

Phase 1

We intend to recruit 20 employed individuals with ASD and 20 employed individuals with IDD to complete in depth qualitative interviews, 100 employed individuals with ASD and 100 employed with IDD to complete **quantitative** perceptual mapping surveys. We will recruit 40 individuals 10 ASD 10 IDD, 10 vocational staff, and 10 from the project Advisory Board to conduct vector modeling analysis with and complete sample messaging. We aim to recruit at least 120 participants with ASD and 120 participants with IDD for the pilot SAFE program, which we anticipate will yield a total of 96 participants in the final sample when accounting for 20% attrition rates commonly identified in prior intervention studies of people with ASD and/or IDD.

Phase 2

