We will recruit 60 individuals—30 with IDD and 30 vocational staff—to participate in focus groups aimed at identifying stakeholder priorities for additional health communication related to staying safe from infectious airborne diseases and ensuring workplace safety. Focus groups will ideally include 5-10 people, but that they may be as small as 1, thus turning it into an interview instead.

The project team will recruit 5-10 staff members from community partners listed above to participate in a pilot training session. Following the training, staff

SAFE Protocol

member participants will provide feedback to inform any necessary revisions to the training materials or processes, ensuring the content is effective and practical for future use. The additional lessons will be developed based on feedback from the focus group. Once completed, the materials (including recruitment materials) will be submitted as an amendment to the IRB and will not be used until approval is granted. After IRB approval, the materials will be provided to the staff and used in the training.

This will require between 2-3 one to two hour sessions.

a) Inclusion and Exclusion Criteria

We anticipate recruiting young adults 18 years old and over with ASD or IDD who are currently employed or actively looking for employment to participate in the study. Participants will have a diagnosis of ASD or IDD. Participants will self-report their ASD or IDD diagnosis. Additionally, the community agencies have access to documentation that identifies their consumer's diagnoses. Based on this, we will ask them to only provide information to those individuals who have a diagnosis of IDD. Potentially eligible participants with documented intellectual and developmental disabilities will be recruited through large vocational rehabilitation organizations (Community Integration Services [CIS] and Project Search) that together serve over 1200 adults with IDD. Participants must be working a minimum of 10 hours a week outside the home and/or receive vocational rehabilitation services. We aim to recruit at least 120 participants, which we anticipate will yield a total of 96 participants in the final sample when accounting for 20% attrition rates commonly identified in prior intervention studies of people with ASD/IDD.

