We intend to complete the **SAFE program** and interviews over the course of three years starting as soon as IRB approval is obtained. We intend to complete the qualitative interviews and quantitative surveys in the first year. We intend to implement the SAFE program until approximately 120 participants have completed the program and data collection during year two and three. Recruitment will occur throughout the course of the study until the targeted number of participants is obtained. We will use block randomization, which will allow us to have continuous enrollment in the study.

Participation in the **SAFE program** is completed over the course of 2-4 weeks.

Participants will meet 2-3 times a week for approximately 60 minutes with either staff, a peer support specialist peer, or occupational therapy graduate students. The meetings will provide direct instruction and role play experiences covering the main concepts and proper use of preventable behaviors to protect against COVID-19 and other airborne diseases in the workplace.

Phase 2

Phase 2 will be completed over the course of one year following IRB approval. During the first two months, recruitment for the focus groups will take place. In months 2-4, focus groups will be conducted, and their feedback will be analyzed. Months 4-8 will involve revising the SAFE curriculum by adding lessons based on the focus group feedback. The final months will focus on recruitment and training.

Study Procedures and Data Analysis

Procedures.

To assess perceptions of peer-support interventions and use of preventative decision-making practices for individuals with ASD and or IDD in the workplace we will conduct in-depth qualitative interviews with individuals with ASD and or IDD working 10 hours or more a week (n=20 or until data saturation) who receive employment services or supports in order to: 1) understand the barriers and facilitators of implementing preventative decision-making practices for IADs and individuals with IDD in the workplace; 2) examine the perceptions and acceptability of peer support intervention strategies; and 3) develop a perceptual mapping survey instrument based on these findings.

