If the participant is assigned to the staff intervention support staff will be contacted with an email or phone call. Staff members will be required to complete human subjects training. Researchers will obtain informed consent for all participants. During the first contact made with participants, written information will be provided remotely using Zoom/FaceTime or in person to all participants explaining the following in simple terms: 1) the criteria for participation, 2) the purpose of the research and the procedures involved, 3) the subject's right to withdraw at any time without penalty of any sort, 4) potential benefits to the subject, 5) potential risks, 6) assurance of anonymity, and 7) terms of remuneration. All research staff will complete training about the informed consent process prior to consenting subjects. The information described above will be reviewed and any questions answered. Participants will be obtained signed or a printed signature box used for signature when electronic signatures are unable to be obtained for consent either in person or virtually.

We will collect data from young adults or transitional aged-youth with ASD or IDD to determine the efficacy and feasibility of the intervention. Recruitment occurs through the sites identified in the participant recruitment section of this proposal. Participants interested in the study will contact the primary investigator or research staff who will schedule an initial physical or virtual meeting at a place and time convenient for the participant to determine inclusion and obtain consent/assent. Participants are randomly assigned to either peer-support intervention, staff intervention or a control group. We will randomize in blocks of 12 (4 to each group) until we reach the targeted number of 120 or

SAFE Protocol

40 participants in each group. Pre-test and post-test measures will be administered by researcher staff prior to the start of the intervention (Pre-test) and at the end of the intervention 4 weeks (Post-test). Key stakeholders, including the participants and interventionists (occupational therapists and peer mediators), will complete qualitative interviews at the end of the intervention period for each participant. The information gathered will determine acceptability and feasibility of intervention. Participants will be asked to discuss their experiences during the intervention specific to their assigned intervention group.

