Based on the feedback received, research staff will make any necessary revisions to ensure the materials are both effective and accessible.

Once finalized, the new content will be integrated into the existing SAFE program materials. Research staff will adapt the content into various formats, including written guides, videos, and infographics, to meet the diverse learning needs of participants.

Pilot Testing for Service Providers

- Research staff will recruit 5-10 staff members from a large service provider organization to participate in pilot testing of the training materials. This pilot testing will occur over a 1-2 month period, during which staff will be trained on the new SAFE materials and additional content. The trainings will occur using Zoom meetings. The training sessions will be conducted either in groups or individually, depending on scheduling availability. Feedback will be collected from participants through surveys, interviews, or debriefing sessions to evaluate the effectiveness of the training. The training feedback will be audio recorded to ensure that we capture all important information you share. The audio recordings will be transcribed by the project team using Zoom's transcription feature. By signing the consent form, you are giving permission to be recorded.
 - Only people working on this project will have access to the recordings.
 - Information and transcripts will be stored securely in locked filing cabinets or on password-protected computers.

Based on this feedback, research staff will refine the training materials and curriculum, making necessary adjustments to improve clarity, accessibility, and applicability. These

SAFE Protocol

trainings will not be recorded. Feedback will only be collected using FIM surveys, AIM surveys and exit interview.

Once these refinements are complete, the finalized curriculum will be prepared for broader implementation within service-based organizations that support individuals with IDD. Participants will receive \$50 for the training. Participant will receive \$25 after the first training sessions and an additional \$25 after completion.

Data Analysis. Descriptive statistics including mean, median, standard deviation, skewness, frequencies, and percentages will be computed on demographic and measures as appropriate. We will complete ANOVAs to determine if there were significant changes in scores on outcome measures within and between groups. We will use SPSS to complete the analyses.

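### The plan expects 20% attrition but sets no analysis population, missing-data rule or post-test follow-up for people who stop sessions, so SAFE-versus-control may be biased in an unknown direction

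*Combined protocol and SAP*

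**What the plan says.** Four places in the combined protocol and SAP bear on who is analysed.

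- **Inclusion and Exclusion Criteria (9a):** "We aim to recruit at least 120 participants, which we anticipate will yield a total of 96 participants in the final sample", allowing for 20% attrition. No rate is given by arm.
- **Study Timelines (9b), Phase 1:** the program runs "until approximately 120 participants have completed the program and data collection".
- **Study Procedures and Data Analysis, Procedures:** randomisation is 1:1:1 to peer support, staff delivery or control, in blocks of 12, up to 120 people, or "40 participants in each group". A pre-test precedes the intervention and a post-test follows at 4 weeks.
- **Data Analysis:** "We will complete ANOVAs to determine if there were significant changes in scores on outcome measures within and between groups", using SPSS.

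The documents name no analysis population and no method for missing data. The section on withdrawal (9c) lets people leave at any time, but does not separate stopping sessions from stopping data collection. Retention appears only as a feasibility benchmark, under Feasibility Data.

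**The concern.** A conventional pre/post ANOVA uses only people with both scores. If 24 of 120 have no post-test, the comparison rests on the other 96, and randomisation no longer guarantees that the arms are alike.

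The arms ask different things of participants. The SAFE arms meet 2-3 times a week for 2-4 weeks, while controls keep their usual vocational supports and have no sessions to drop out of. The section on risks (11) says that the interaction may be felt as stressful, especially by people with social and communicative challenges. That is a plausible reason for leaving which arises mainly in the SAFE arms and is related to outcomes such as anxiety, stress and self-efficacy. If it operates, the SAFE-versus-control contrasts behind research questions 1 and 2 could be shifted with no true effect present. Post-tests that are not collected cannot be recovered later.

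**Working it through.** **1. The plan's own figure.** 120 × (1 - 0.20) = 96. This reproduces exactly, and is 32 per arm if dropout is equal (40 × 0.80).

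**2. The competing counts.**
- If about 120 people must complete, 20% attrition requires 120 / 0.80 = 150 randomised, against the 120 in the randomisation text. Controls have no program to complete, so this count cannot apply to all three arms.
- Recruitment Methods says "We aim to recruit at least 120 participants with ASD and 120 participants with IDD for the pilot SAFE program" and gives the same final sample of 96. But 240 × 0.80 = 192, and reaching 96 from 240 would need 60% attrition.

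**3. General size of the bias.** Let *d* be an arm's dropout rate, and *D* the mean post-test difference, in SD, between those who stay and those who leave. The mean among stayers exceeds the mean of the full arm by d × D, so

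bias = d(SAFE) × D(SAFE) - d(control) × D(control).

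The splits and values of D below are assumptions. The total is held at 96, with equal dropout in the two SAFE arms and the same D in every arm.

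| Control / SAFE dropout | Analysed (control, SAFE, SAFE) | D = 0.25 | D = 0.5 | D = 1.0 |
|---|---|---|---|---|
| 20% / 20% | 32, 32, 32 | 0 | 0 | 0 |
| 10% / 25% | 36, 30, 30 | 0.04 | 0.08 | 0.15 |
| 0% / 30% | 40, 28, 28 | 0.08 | 0.15 | 0.30 |

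For one SAFE-versus-control test at an assumed two-sided 5%, the false-positive rate is about 6% (10%/25%, D = 0.5), 9% (0%/30%, D = 0.5) and 23% (0%/30%, D = 1.0). Equal rates protect only if the leavers are alike: with 20% in both arms but D = 0.5 in SAFE and 0 in control, the bias is 0.20 × 0.5 = 0.10 SD.

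**4. Direction.** This is a simulation with no true effect. Assumed dropout is 27%, 27% and 6% (mean 20%), with log-odds of dropout rising by 1 for each SD of lower baseline score. The assumed pre-post correlation r is 0.5 or 0.7.
- Baseline gap among stayers, SAFE minus control: 0.17 SD.
- Post-test bias: +0.085 (r = 0.5) and +0.120 (r = 0.7). As a check, r × 0.17 = 0.085 and 0.119.
- Change-score bias: -0.083 and -0.049. As a check, (r - 1) × 0.17 = -0.085 and -0.051.
- Baseline-adjusted bias: about 0.
- Peer versus staff: 0, because both arms lose 27%.

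**5. The same rates and slope, with dropout driven by the post-test score.**
- Baseline-adjusted bias: +0.13 (r = 0.5) and +0.09 (r = 0.7).
- Change-score bias: +0.09 and +0.05.

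**6. Precision.** If 24 post-tests are missing, standard errors widen by sqrt(120/96) = 1.118, about 12%. Changing the model alone does not recover this.

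**The case against.** A reader might infer that the plan restricts the ANOVA to people who completed the program. No sentence says so. The 96 is an ordinary attrition allowance, the completer count stands in a timeline section, and controls cannot be program completers, so completion cannot be the criterion for analysis in all arms. Someone who stops sessions but takes the post-test could be included. This objection stands in full. What is missing is any rule, and the default of the method then decides.

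A reader might also infer that dropout will flatter SAFE. The documents do not support that. The Data Analysis sentence speaks of changes in scores, and under baseline-related dropout the change-score bias runs against SAFE.

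Unequal dropout is itself an assumption. The protocol gives one overall rate, screens for ability to engage in learning, allows a proxy, and permits delivery remotely or at the workplace. In the 27%/27%/6% scenario the error rate is modest. With about 29 and 38 analysed (40 × 0.73 and 40 × 0.94), the standard error is about 0.19 to 0.25 SD, so a nominal 5% test becomes about 6% on change scores and 6 to 8% on post-test scores.

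Finally, this is described as proof of concept, and the randomisation text already sets 120 as the number randomised. These points lower the stakes. They do not supply an analysis population or a follow-up rule.

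**Conclusion.** The point holds as a gap in the plan and a risk of bias, not as a demonstrated bias. The plan anticipates losing 24 of 120, names an analysis that by default omits people without a post-test, and does not ask for that post-test from those who stop attending.

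Under the assumed splits the bias in SAFE versus control runs from 0 to about 0.30 SD. In the more specific scenario it is about +0.09 to +0.12 SD on post-test scores and -0.05 to -0.08 SD on change scores. The sign depends on which ANOVA is meant and on what drives dropout, and the plan settles neither. Peer versus staff (research question 3) is unaffected if those two arms lose similar people at similar rates. Every dropout rate by arm, correlation and selection strength used here is an assumption.

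Separately, the counts of about 120 completed, 120 randomised and 96 in the final sample do not fit together as written. This should be corrected, with medium confidence as to its practical effect.

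**What to change.** 1. Seek the 4-week post-test from every randomised participant whatever their attendance, unless they withdraw from data collection. Record the two kinds of withdrawal separately. This is the key step, because no model fully repairs dropout that depends on unseen scores.
2. Make the main analysis all randomised participants by assigned arm, using a linear mixed model of pre-test and post-test with a common baseline mean across arms (SPSS MIXED). This removes the bias when dropout depends on baseline, but not when it depends on the post-test.
3. Add a sensitivity analysis for that second case. For example, impute missing post-tests with a downward shift over a stated range, such as 0.25 to 1.0 SD, by arm.
4. Report dropout by arm, and show program completers as supportive only.
5. Reword Study Timelines to agree with the randomisation text: 120 randomised, about 96 expected with a post-test. Reconcile the 120 plus 120 in Recruitment Methods at the same time.

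The cost is some follow-up calls, a different SPSS procedure and a few paragraphs of text. The estimated effect may be smaller, because it will include people who attended few sessions.

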Perceptual Mapping Survey Development. Once qualitative data is analyzed, we will develop a perceptual mapping survey using the themes from the interviews. Surveys are constructed using statement blocks with 5 to 7 related statements each. Participants indicate how much they agree or disagree with a statement using a 0 to 10 scale (0=totally disagree, 10=totally agree). For example, barriers statements may include “I do not think I am at risk of getting an infectious airborne disease” or “I don’t trust that masks really protect me.” Other statement groups might include facilitators to or beliefs about preventive behaviors, such as “I believe that standing six feet from someone can protect me”. These surveys are set up to reflect how study elements are conceptualized relative to each other and relative to “Self”, based on the mean scores of the group being studied. Then perceptual maps are constructed for each block.

Refine peer-support components of the *SAFE program* intervention and assess feasibility and acceptability of program components based on vector modeling findings. We will: 1) Conduct surveys with individuals with ASD and or IDD working 10 or more hours a week (n=100); 2) Conduct vector modeling analysis to identify: a. acceptable and feasible peer-support strategies *and* b. messages around preventative decision-making processes for airborne diseases in the workplace; 3) Concept-test refined strategies and messages with individuals with ASD and IDD working 10 hours a week (n=10), vocational rehabilitation staff (n=10), and the project Advisory Board (n=10) for feedback on acceptability; and 4) Refine intervention materials, fidelity processes and conduct usability testing with the same groups to assess potential feasibility of the intervention.

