Perceptual Mapping Survey Analysis and Vector Message Modeling. We will be responsible for the analysis of quantitative data from the survey to construct perceptual maps. These maps will be created using multidimensional scaling (MDS) software developed based on the Galileo system (The Galileo Company, 2018). Input associations among the risks/benefits are derived from the inter-item correlations. The software then performs a metric MDS analysis and produces graphic arrays of the distances among the elements to produce a 3-dimensional map (Figure B). A percentage of explained variance is calculated as an index of the explanatory power of the map, showing validity of the method. The software is highly valid; if you enter distances between American cities into the program, a map that shows the cities in proper relative positions to each other, including longitude and latitude, is constructed with very little error (SSTRESS = .003). Possible differences in perceptual maps by subgroup will be assessed using k-mean cluster analyses. This “segmentation”, usually by psychographic variables such as perception variables or demographics (gender, age etc.), is important to understand potential perceptual differences by segment. Should differences exist, maps will be generated separately for subgroups to assess whether significant differences would impact message design and incorporated into the *SAFE program*. Surveying 150-200 people with ASD and IDD should be adequate to do this sub-analysis if needed.

Once perceptual maps are constructed, we will conduct vector analyses to design messages that optimize the fit between people with ASD’s perceptual maps and the *SAFE program* intervention content. These messages will be embedded in the intervention to help people with ASD and IDD make positive, protection decisions about measures that will reduce their risk of IAD transmission. To do this, the software

SAFE Protocol

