determines optimum strategies to emphasize in a message, including both the positive and negative attributes that should be moved and where in the space they should be repositioned to “pull” the group (see dotted lines in Figure B) toward the behavior (in this case, mask wearing). Mathematically, this defines the “target vector”. This is then used to create message strategies to use in an intervention. For this study we will construct maps with multiple targeted vectors, including mask wearing, social distancing, and hand washing/hand sanitizing. While the construction of the message is left to the researcher, the content of the messages is made clear by the modeling. Once these messages are constructed, we will integrate them into the existing **SAFE program** intervention and develop processes to evaluate fidelity to the intervention. We will then “concept test” these with our advisory board to assess salience, acceptability and understanding.

Concept testing. To confirm whether the mapping strategies are salient to individuals with IDD and/or ASD, we will conduct concept testing with participants including working individuals with ASD (n=10) and IDD (n=10), vocational rehabilitation staff (n=20), and the project Advisory Board (n=20). The project Advisory Board is made up of 10 stakeholders including working individuals with ASD, family or caregivers, researchers and staff or administrators from employment service providers. We will develop a testing interview guide based on the Feedback Sessions Toolkit⁸⁰ for testing health communication messages. These groups will assess salience, understanding and acceptability. All interviews will be audio-recorded and analyzed. Once these messages are constructed study staff to integrate messages into the **SAFE program** content.

We will collect data using quantitative and qualitative interviews. We will use surveys to obtain demographic, general COVID-19 knowledge, self-advocacy/self-determination and workplace safety information. We will conduct qualitative interviews to determine acceptability and feasibility of intervention. Participants will be asked to discuss their experiences during the intervention specific to their assigned intervention group.

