PROMIS General Self-Efficacy Item Bank. This measure assesses a person’s belief in their capacity to manage daily stressors and have control over meaningful events. Participants will complete the 10-question tool which is designed for people 18 years and older. It has established acceptable reliability and validity.⁸¹ The responses are on a 5 point scale from “I am a little confident” (1) to “I am very confident” (5) with higher scores reflecting greater general self-efficacy. A total standard T-score will be used to analyze the data.

VocFit Safety Subscale. The VocFit is an assessment tool used to measure the best fit for a worker with a job.⁸ The tool was specifically developed for individuals with developmental disabilities and has strong psychometric properties for this population.⁸² The VocFit safety subscale consists of 8 questions asking to what degree the participant demonstrates the ability to engage in safety protocol at their employment. The tool identifies the degree to which the participant is able to follow safety protocols and precautions in their work setting. The response options include “high”, “some”, and “low”.

Workplace Health and Safety Self-Advocacy Scale (WHSSS). This measure was adapted from employment-centered items on the Self-Determination and Self-Advocacy Questionnaire, which assesses the degree of self-advocacy in the workplace as reported by staff and self-reported by participants. The measure has ten questions and takes 5-10 minutes to complete. The modified WHSSS assesses the skills used to advocate for preventative practices for IADs in the workplace and the degree to which the person uses these skills. The response options range from “none of the time” (1) to “all of the time.”

Perceptual Survey Items. To assess perceptions of IADs and protective behaviors, we will utilize the perceptual mapping items developed in the formative phase. These will be determined at baseline and the one-month follow-up to see if perceptions have changed based on intervention content. We will be able to compare perceptual maps of interventions groups to see if specific messaging affected the relationship between the group and the target protective behavior.

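### The plan names two different inputs (group means and inter-item correlations) for the perceptual-map distances, and map position should not serve as evidence that the intervention changed perceptions

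*Combined protocol and SAP*

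**What the plan says.** Three places in the protocol bear on this.

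- **Section 9, Perceptual Mapping Survey Development.** "Surveys are constructed using statement blocks with 5 to 7 related statements each". Agreement with every statement is rated from 0 to 10. The surveys are said to show "how study elements are conceptualized relative to each other and relative to “Self”, based on the mean scores of the group being studied", and one map is built per block.
- **Section 9, Perceptual Mapping Survey Analysis and Vector Message Modeling.** "Input associations among the risks/benefits are derived from the inter-item correlations". These feed a metric multidimensional scaling that yields a three-dimensional map. The plan does not say how a correlation becomes a distance, or how means and correlations enter one distance matrix.
- **Measures, Perceptual Survey Items.** "These will be determined at baseline and the one-month follow-up to see if perceptions have changed based on intervention content". The next sentence plans to compare the maps of the intervention groups, to see whether messaging altered where the group stands relative to the behavior being promoted.

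The Data Analysis paragraph plans ANOVAs on outcome-measure scores within and between groups. Total or T-scores are defined for several instruments under Measures, but none is defined for the perceptual items.

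**The concern.** For distances between elements, one section names group means and the other names correlations. These are not interchangeable. A mean records how far people agree; a correlation records only whether people who agree more with one statement also agree more with another. Messages are meant to move the level of agreement. Where a distance is built from correlations, that movement does not enter it.

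The issue would be minor if the maps served only to design messages. The plan also uses them to compare arms after the intervention. If the fitted distance between the group and the target behavior reflects a mixture of two incompatible inputs, the reader cannot tell whether a difference between arms is a difference in belief or a by-product of the scaling.

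**Working it through.** The plan gives no figure for the maps that could be reproduced, so the check is algebra followed by a simulation.

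**1. Algebra.** For any constants a and b, corr(X + a, Y + b) = corr(X, Y). A uniform shift without floor or ceiling therefore leaves every correlation as it was. In simulation the largest change was 3e-16, which is rounding error. This needs no assumption about spread, loadings or sample size.

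**2. Simulation under the most favorable reading.** Self distances come from means, statement distances from correlations.

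- From the plan: 0 to 10 scale, 5 to 7 statements per block (6 used), metric scaling in 3 dimensions, 40 per arm (40 × 0.8 = 32 after 20% attrition).
- Assumed: 200,000 respondents; 3 belief statements, 2 barriers, 1 target behavior; baseline mean 5; SD 2; one common factor with absolute loadings 0.6 to 0.7; answers rounded and capped; classical scaling; statement distance 5(1 − r); Self distance 10 − mean.
- Beliefs and target shift up, and barriers down, by the same amount for everyone.

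| Shift | r, belief–target | 5(1 − r) | Self–target input | Self–target fitted |
|---|---|---|---|---|
| 0 | 0.476 | 2.62 | 5.01 | 4.70 |
| 1 | 0.475 | 2.63 | 4.02 | 3.67 |
| 2 | 0.470 | 2.65 | 3.06 | 2.54 |
| 3 | 0.459 | 2.70 | 2.17 | 1.47 |
| 4 | 0.436 | 2.82 | 1.39 | 2.28 |

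Up to 3 points the fitted distance falls as it should. From 3 to 4 points agreement increases further and the input falls, but the fitted distance rises. A repeat run under similar assumptions gave 1.64 to 2.70 with 5(1 − r), and 4.49 to 4.87 with √(2(1 − r)).

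**3. Why it reverses.** At a shift of 4 the inputs cannot all hold in one space. Self lies 1.39 from a belief and 1.39 from the target, so those two can be at most 1.39 + 1.39 = 2.78 apart, but the correlation sets them 2.82 apart. Barrier–target r is −0.373, giving 5 × 1.373 = 6.87. Self to barrier can then be at most 1.39 + 6.87 = 8.26, but the means give 8.61. At a shift of 3 both conditions are met (2.70 against 4.34; 7.84 against 2.17 + 5 × 1.394 = 9.14). With √(2(1 − r)) the conflict is larger: at a shift of 4, barrier–target is √(2 × 1.373) = 1.66, so the bound is 1.39 + 1.66 = 3.05 against 8.61.

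**4. Uneven response.** Let half the group shift by 4 and half by 0, a nominal average of 2. With 5(1 − r), belief–target r rises to 0.735, the Self–target input is 10 − 6.80 = 3.20, and the fitted distance is about 3.1. The uniform 2-point shift gave input 3.06 and fitted 2.54. The inputs differ by 0.14 and the fitted distances by about 0.6. With √(2(1 − r)) this gap nearly disappears.

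**5. Ceiling drift against noise.** A uniform 3-point shift lowers r by 0.476 − 0.459 = 0.017. The standard error of one correlation is (1 − r²)/√(n − 1): 0.774/√39 = 0.12 at n = 40 and 0.774/√31 = 0.14 at n = 32. The drift is about one-seventh of a standard error or less.

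**The case against.** The strongest reply is that the two sections can be read together. Correlations are named only for associations among risks and benefits, while position relative to Self is tied to "based on the mean scores of the group being studied". The planned comparison is of the group with the target behavior, which is a Self distance. Under 5(1 − r) it tracks shifts of 1 to 3 points. This stands, and it rules out a stronger reading that a reader might draw from the correlation sentence alone: that a real shift in belief always leaves the map unchanged or moves it the wrong way. The documents do not support that. Nor is it general even for statement distances, since an uneven response raised r and drew beliefs toward the target.

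A second reply is that the sentence on baseline and one month refers to the items rather than the maps, and that the perceptual items appear under the primary outcome measures, so the planned ANOVAs may already cover their scores. That is possible. But no score is defined for these items, and the only comparison between groups stated for them is of maps.

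Third, the transform, the software's fitting algorithm and any alignment of maps across visits or arms are not given, so the reversal is shown under assumed choices only. This limits what can be said about size. It does not settle which input applies. Finally, none of the three numbered research questions rests explicitly on the maps, which limits the consequence.

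**Conclusion.** The concern holds in limited form. The plan gives two inputs for element-to-element distances without reconciling them, and correlation-based distances cannot register level of agreement; that last statement is exact. Even on the favorable reading, joint scaling can distort the group-to-behavior distance. In the run shown, it rose by 2.28 − 1.47 = 0.81 while the mean-based input fell by 2.17 − 1.39 = 0.78, and two response patterns with nearly the same mean gain differed by about 0.6. These sizes rest on the assumed transform, loadings, SD and baseline mean, and the second feature was seen clearly under only one of two transforms.

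A reader might also infer that ceiling effects in the correlations will by themselves mislead the trial. At 32 to 40 per arm they are lost in sampling noise unless shifts are very large. The point is worth correcting before analysis because the maps are given a role as evidence of effect that their construction cannot be relied on to bear.

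**What to change.** - **Perceptual Survey Items.** Base the conclusion that perceptions changed, and the comparison between arms, on statement or block mean scores at follow-up by arm, adjusted for the pre-test score. Define the score, and name it in the Data Analysis paragraph.
- **The two survey sections.** Say which distances use means and which use correlations, how Self is placed, and the transform from correlation to distance.
- **Role of the maps.** Keep them for message design and description. State that neither map position nor re-estimated statement-to-statement distances will be read as evidence of changed belief.

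Holding the statement configuration fixed from pre-test data may look like an alternative, but it does not remove the distortion: from a 3- to a 4-point shift the fitted Self–target distance still rose, from 1.66 to 2.31 with 5(1 − r) and from 4.50 to 4.86 with √(2(1 − r)).

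The cost is a few sentences and one extra table of means, from data already to be collected. The maps lose their role as evidence of effect.
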